7.3.2.1. Pharmacokinetics

The PK analysis set will include all randomized subjects who took at least one dose of study drug and for whom concentration data of EFX is available.

7.3.2.2. Biomarkers

The Biomarker Analysis Set will include data from subjects in the Safety Analysis Set who have the necessary baseline and on-study measurements to provide interpretable results for the specific parameters of interest.

7.4. Data Handling Conventions

Missing data can have an impact on the interpretation of the trial data. In general, values for missing data will not be imputed.

Where appropriate, safety data for subjects that did not complete the study will be included in summary statistics. For example, if a subject received study drug, the subject will be included in a summary of AEs according to the treatment received; otherwise, if the subject is not dosed then they will be excluded from the summary. If safety laboratory results for a subject

are missing for any reason at a time point, the subject will be excluded from the calculation of summary statistics for that time point. If the subject is missing a pre-dose value, then the subject will be excluded from the calculation of summary statistics for the pre-dose value and the change from pre-dose values.

Values for missing safety laboratory data will not be imputed; however, a missing baseline result will be replaced with a screening result, if available. If no pre-treatment laboratory value is available, the baseline value will be assumed to be normal (i.e., no grade [Grade 0]) for the summary of graded laboratory abnormalities.

Values for missing vital signs data will not be imputed; however, a missing baseline result will be replaced with a screening result, if available.

Further details of data handling conventions and transformation will be provided in the SAP.

7.5. Demographic Data and Baseline Characteristics

Demographic and baseline measurements will be summarized using standard descriptive methods.

Demographic summaries will include T2D status, sex, race/ethnicity, and age.

Baseline data will include a summary of body weight, height, BMI, waist-to-hip ratio, randomization stratification groups, and other disease characteristic variables.

7.6. Efficacy Analysis

7.6.1. Primary Efficacy Analysis

The primary efficacy variable will be the absolute change from baseline hepatic fat fraction measured by MRI-PDFF at Week 12. Summary statistics (number of subjects, mean, standard deviation, median, minimum, and maximum) at all visits and change from baseline will be provided. The primary efficacy analysis will be analyzed with an analysis of covariance (ANCOVA) model with treatment group and F1 fibrosis score as factors and baseline hepatic fat fraction measured by MRI-PDFF as a covariate. For any subjects in the full analysis set (FAS) with a missing primary efficacy value, the primary efficacy variable will be imputed with multiple imputation method. The specification of the multiple imputation method will be provided in the SAP. The treatment effect of each active dose comparing with placebo will be estimated from the ANCOVA model. LS means, one-sided, 97.5% confidence intervals and one-sided p-values will be calculated. In order to control the Type I error rate inflation caused by multiplicity issues, a step-down fixed hypothesis testing sequence will be used. That is, only high dose is proved to be significantly better than placebo will the next low dose be compared.

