The safety of EFX will be assessed during the study through the reporting of adverse events (AEs), clinical laboratory tests, electrocardiogram (ECG), vital sign assessments, body weight, anti-drug antibody (ADA) and neutralizing antibody (NAB) assessments, and concomitant medication usage.

An external Data Monitoring Committee (DMC) that consists of two hepatologists, one cardiologist, and a statistician will review the progress of the study. The DMC will convene after 20 subjects (approximately 5 per treatment group in the Main Study) have completed the Week 4 assessments. The DMC will receive all reports of serious adverse events (SAEs) and convene as needed to monitor for safety.

Pharmacokinetics:

Blood for pharmacokinetics (PK) will be collected at specified timepoints after dosing as outlined in the Schedule of Assessments (Appendix A and Appendix B) and will be used to estimate steady state PK parameters (i.e., T_{max} , C_{max} , C_{trough} , AUC_{0-t}, $t_{1/2}$, CL/F, Vz/F) following subcutaneous (SC) administration of EFX.

Efficacy:

Main Study:

The efficacy will be assessed via the absolute change from baseline in hepatic fat fraction measured by MRI-PDFF at Week 12.

Cohort C:

The efficacy will be assessed via the change from baseline in liver stiffness as evaluated by FibroScan® at Week 16 and non-invasive plasma (serum) fibrosis biomarkers including Liver Fibrosis by ELFTM Test score and pro-C3 levels.

Sample Size Calculation:

Main Study:

With the following assumptions, the power for N = 20 subjects with active treatment is approximately 91% to detect:

- a true, baseline-adjusted, mean decrease from baseline in MRI-PDFF-estimated hepatic fat content of 5% (absolute) compared to placebo,
- with a one-sided t-test for decrease from placebo,
- at a 5% significance level,
- 20 subjects receiving placebo, and
- a standard deviation estimated as 5.2% (Sanyal et al. 2019).

Cohort C:

Since the primary objective for Cohort C is to assess the safety and tolerability of EFX in NASH subjects with compensated cirrhosis, the sample size of Cohort C is determined based on clinical considerations, and the treatment comparisons of efficacy measurements are not powered.

Statistical Methods:

Efficacy Analysis:	Primary Efficacy Analysis (Main Study Only):

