7.10. Sample Size

Main Study:

Due to the exploratory nature of this study, no formal power calculations were used to determine sample size. The number of subjects was chosen based on clinical experience with other similar proof of concept studies.

With the following assumptions, the power for N = 20 subjects with active treatment is approximately 91% to detect:

- a true, baseline-adjusted, mean decrease from baseline in MRI-PDFF-estimated hepatic fat of 5% compared to placebo,
- with a one-sided t-test for decrease from placebo,
- a 5% significance level,
- 20 subjects receiving placebo, and
- a standard deviation estimated as 5.2% (Sanyal et al. 2019).

Cohort C:

Since the primary objective is to assess the safety and tolerability of EFX in NASH subjects with compensated cirrhosis, the sample size is determined based on clinical considerations, and the treatment comparisons of efficacy measurements are not powered.

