### 1 INTRODUCTION

The purpose of this Statistical Analysis Plan (SAP) is to provide a description of the statistical methods to be implemented for the analysis of the Cohort C data from Akero Therapeutics, Inc. Protocol AK-US-001-0101. A separate SAP has been provided for the analysis of Main Study data from Akero Therapeutics, Inc. Protocol AK-US-001-0101. The SAP will be finalized prior to unblinding of the Cohort C database. Any deviations from the SAP after database unblinding will be documented in the final Clinical Study Report (CSR).

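### The Main Study primary analysis sets no alpha: Section 7.6.1 pairs a significance-gated dose sequence with one-sided 97.5% intervals, while the power statement assumes one-sided 5%

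*Protocol*

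**What the plan says.** Protocol Section 7.6.1 defines the primary analysis of the Main Study: an ANCOVA of the absolute change in hepatic fat fraction at Week 12, comparing each EFX dose with placebo. On inference it says: "LS means, one-sided, 97.5% confidence intervals and one-sided p-values will be calculated". Multiplicity is handled by a step-down fixed sequence, described as: "only high dose is proved to be significantly better than placebo will the next low dose be compared". Neither this section nor the Synopsis text on the primary analysis gives the level at which a dose counts as significant.

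A level appears only in the power statements. Section 7.10 says that "the power for N = 20 subjects with active treatment is approximately 91% to detect" a 5-point difference, "with a one-sided t-test for decrease from placebo", at "a 5% significance level". The Synopsis repeats this ("at a 5% significance level"). Section 7.10 opens with a caveat: "Due to the exploratory nature of this study, no formal power calculations were used to determine sample size".

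The SAP reviewed here covers Cohort C only. Its introduction states: "A separate SAP has been provided for the analysis of Main Study data". Its general rule in Section 3.1.5 (two-sided 0.05 for parameters of neutral direction) therefore does not govern the Main Study primary test.

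**The concern.** A one-sided 97.5% confidence bound excludes zero exactly when a one-sided test is significant at 2.5%. The power statement uses a one-sided test at 5%. These are different decision rules for the same comparison, and the section that applies the rule does not say which one holds.

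Two things follow on the protocol text.

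- **The gate is undefined.** If 70 mg gives a one-sided p-value between 0.025 and 0.05, then 50 mg is compared under one reading and the sequence stops under the other. The same can happen between 50 mg and 28 mg. A fixed sequence controls the family-wise error at whatever level is used at each step, so that level has to be fixed before unblinding.
- **The report can disagree with itself.** If 5% governs, a dose can be declared significant beside an interval that includes no effect. If 2.5% governs, the 91% does not describe the planned test.

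**Working it through.** **Inputs** (Protocol Section 7.10, repeated in the Synopsis): true difference 5 points, SD 5.2 points, 20 subjects on the active dose, 20 on placebo, one-sided t-test. Differences are written as reduction versus placebo, so positive favours EFX.

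**Standard error and noncentrality**

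- SE = SD × √(2/n) = 5.2 × √(2/20) = 1.644 points
- Noncentrality = 5 / 1.644 = 3.041

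**Reproducing the stated power, then changing only alpha.** Power is the probability that a noncentral t exceeds the critical value. The two-sample t-test has 20 + 20 − 2 = 38 df. The planned ANCOVA (four groups, F1 factor, baseline covariate) has 80 − 6 = 74 residual df if all 80 subjects are analysed. The smallest significant observed difference is the critical t × SE.

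| One-sided alpha | df | Critical t | Smallest significant difference | Power at 5 points |
|---|---|---|---|---|
| 5% | 38 | 1.686 | 2.77 | 91.0% |
| 2.5% | 38 | 2.024 | 3.33 | 84.2% |
| 5% | 74 | 1.666 | 2.74 | 91.4% |
| 2.5% | 74 | 1.993 | 3.28 | 85.1% |

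The protocol's 91% is reproduced at one-sided 5% and not at 2.5%, so the 5% in Section 7.10 was really used and is not a misprint.

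**Where the two levels disagree.** They give opposite answers for observed differences from 2.77 to 3.33 points (2.74 to 3.28 with the ANCOVA df).

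**Example inside the zone: observed difference 3.0, 38 df**

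- t = 3.0 / 1.644 = 1.824, one-sided p = 0.038: significant at 5%, not at 2.5%
- One-sided 97.5% lower bound = 3.0 − 2.024 × 1.644 = −0.33: includes zero
- One-sided 95% lower bound = 3.0 − 1.686 × 1.644 = +0.23: excludes zero

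**Chance that a single comparison falls in the zone** (power at 5% minus power at 2.5%, 38 df)

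| True difference | Source of the value | Significant at 5% | Significant at 2.5% | In the zone |
|---|---|---|---|---|
| 0 | no effect | 5.0% | 2.5% | 2.5% |
| 3 | assumed, for range | 55.8% | 42.8% | about 13% |
| 3.9 | Section 1.5, cited FGF21 analogue, weekly: 5.2 − 1.3 | 75.3% | 63.7% | 11.6% |
| 5 | planned, Section 7.10 | 91.0% | 84.2% | 6.8% |
| 5.5 | Section 1.5, same study, daily: 6.8 − 1.3 | 94.9% | 90.3% | 4.6% |

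The Section 1.5 values belong to a different drug and are included only to show the range.

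**Effect along the sequence.** If all three doses truly differ from placebo by 5 points, a simulation with 400,000 replicates and 74 df gives the chance that all three pass as about 81% at one-sided 5% and about 70% at one-sided 2.5%.

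**The case against.** The strongest reply is that the 5% is never declared as the testing level. It is one item in a list of power assumptions, and Section 7.10 says power did not set the sample size. Section 7.6.1 governs the analysis, and its only level is one-sided 97.5%, so a reader could infer testing at 2.5% and treat the 91% as a descriptive figure that was not aligned. That is a reasonable inference, but it remains one: Section 7.6.1 attaches 97.5% to the interval, not to the test or the gate. On that reading the stated power is still about 7 points too high for the planned test.

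Second, the separate Main Study SAP may state the alpha. If so, the gate is clear in practice. This limits the finding to the protocol. In Section 7.6.1 the protocol explicitly leaves the multiple imputation details to the SAP, but it does not do so for the level of the primary test.

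Third, an interval need not match the test, and a one-sided 97.5% bound is also one limit of a two-sided 95% interval. So the interval level would not be an error in itself if 5% governs. It would be a mismatch that allows a significant p-value beside an interval that includes zero. Likewise, the 91% is correctly calculated under its own stated condition.

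Fourth, error control is not lost: the fixed sequence protects the family-wise error at either level, in a Phase 2a study described as exploratory. That stands, and it keeps the point moderate. However, Section 7.6.1 adopts the sequence in order to control the Type I error, and that requires a stated level.

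**Conclusion.** The concern holds. The protocol gives two incompatible levels for the same primary comparison and does not say which one opens the next step of the dose sequence. With SD 5.2 and 20 evaluable subjects per arm, the two levels disagree for observed differences of about 2.8 to 3.3 points. A single comparison lands there with probability 6.8% at the planned difference of 5 points, about 13% at an assumed 3 points, and 2.5% under no effect. Power for one comparison is 91.0% at one-sided 5% and 84.2% at one-sided 2.5% (85.1% with the ANCOVA df).

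These figures treat 5.2 as the residual SD, as the protocol does, and assume no missing data. The zone scales with the actual standard error, which will differ under ANCOVA with multiple imputation. The finding concerns the protocol text; the Main Study SAP was not available to check. It should be fixed, but the design and sample size are not in question.

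**What to change.** State one alpha in Section 7.6.1 and apply it to the p-value, the confidence interval and the step-down gate. Either choice is coherent:

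- **(a) One-sided 0.025.** Keep the one-sided 97.5% intervals and restate the power in Section 7.10 and the Synopsis as about 84%.
- **(b) One-sided 0.05.** Change the intervals to one-sided 95% and keep the 91%.

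Under either option, confirm that the Main Study SAP uses the same level. It would also help to say in Section 7.10 and the Synopsis that the power refers to a single comparison, the first in the sequence. The two-arm description already implies this, so the addition is a clarification.

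The cost is wording only: Section 7.6.1 in both cases, plus the power figure and its alpha in two places under (a). No subjects or visits are added, and N does not change because Section 7.10 says power did not determine it. Option (a) means a less favourable stated power. Option (b) means accepting a 5% one-sided error rate and a less strict interval than the one now planned.

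The level should be fixed before the Main Study data are unblinded; if that has already happened, the report should state which level was prespecified and where.

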7.6.2. Secondary Efficacy Analysis

Main Study:

Akero Therapeutics, Inc.

For the continuous secondary efficacy variables related to hepatic fat fraction, like percent change from baseline in fat fraction measured by MRI-PDFF at week 12, the same ANCOVA model used for primary efficacy variable will be used. For the other continuous secondary efficacy variables, the ANCOVA model with treatment group, baseline hepatic fat fraction (< 15% vs \geq 15%), and F1 fibrosis score as factors will be used. Normality will be tested for the model residuals. For certain efficacy variables, logarithmic transformation may be performed prior to fitting the ANCOVA model.

For the responder(s) based on MRI-PDFF, logistic regression will be used for the analyses. The analyses will include the treatment group and F1 fibrosis score as factors and baseline hepatic fat fraction measured by MRI-PDFF as a covariate. The missing value will be imputed as a non-responder.

For the responder(s) based on the NAS system, Fisher's exact test will be used for the analyses. Odds ratios, 95% confidence intervals and p-values will be provided. The missing value will be imputed as a non-responder.

Cohort C:

Summary statistics (number of subjects, mean, standard deviation, median, minimum, and maximum) at all visits and change from baseline will be provided. The efficacy variables will be analyzed with an ANCOVA model with treatment group as a factor and baseline value as a covariate. The effect of Type 2 diabetes status will be explored. Normality will be tested for the model residuals.

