1.5. Rationale for this Study

Given FGF21's well-documented beneficial effects on metabolic parameters, FGF21 has recently emerged as a promising drug candidate for metabolic diseases, including NASH. FGF21 has many of the key characteristics of an optimal NASH therapy as a result of its well-documented effects in improving insulin sensitivity and lipoprotein levels, reducing liver fat and inflammation, as well as inhibiting fibrosis. In particular, EFX's dual actions of addressing both the underlying NASH disease driver (i.e., increased liver fat and fat oxidation) and downstream NASH pathology (i.e. cellular stress, inflammation and fibrosis), is well suited to patients with F3 and F4 fibrosis, not just patients with early-stage disease. Results from a Phase 2 trial of BMS-986036, an investigational PEGylated analog of FGF21, provide important validation for FGF21 agonism as a NASH therapy (Sanyal et al. 2019). In this study, 74 patients with biopsy-confirmed NASH (stages F1-F3) received 16 weeks of daily or weekly subcutaneous injections of BMS-986036 or placebo. The study achieved its primary endpoint of significant reduction in liver fat versus placebo, as measured non-invasively by magnetic resonance imaging – proton density fat fraction (MRI-PDFF). Absolute fat levels in the daily and weekly dosing cohorts fell 6.8% and 5.2%, respectively, compared to 1.3% in the placebo group. These reductions translated into relative reductions of 38% and 26%, respectively, compared to 6% in the placebo group. Statistically significant improvements were also seen in prespecified exploratory endpoints including biomarkers of fibrosis, lipoprotein parameters and markers of liver injury. Positive changes in Pro-C3, a marker of liver fibrogenesis, and liver stiffness as measured by magnetic resonance elastography, or MRE, were also observed. The addition of Cohort C to the protocol will evaluate the effects of EFX on subjects with cirrhosis using non-invasive imaging and biomarkers of liver fibrosis.

Results from a Phase 2 trial of NGM282, an FGF19 analog, provides additional clinical validation for FGF21 agonism (Harrison et al. 2019). FGF19 and FGF21 are both members of the endocrine subfamily of FGFs. Both have been shown to activate three FGF receptors (FGFR1c/2c/3c) expressed in liver cells (mainly 2c and 3c) and adipose cells (mainly 1c). FGF19 also activates a fourth receptor, known as FGFR4, which FGF21 does not activate.

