In a 12-week clinical trial in NASH patients, a 3 mg daily dose of NGM282 was shown to have a placebo-corrected absolute reduction in liver fat of 11.2% at 12 weeks, or a 67% relative reduction, as measured by MRI-PDFF. This magnitude of liver fat reduction is the largest observed to date in all NASH clinical trials.

Preclinical data suggests that FGF21 agonism of FGFR1c substantially inhibits adipose tissue lipolysis. NGM313, which was developed to mimic FGF21's effects on FGFR1c and β Klotho (but with no activity at FGFR2c and 3c), provides important clinical validation that agonism of FGFR1c substantially reduces liver fat in NASH patients. NGM313 was evaluated in a single-dose, open-label Phase 1b trial in 25 obese, insulin resistant subjects with NAFLD. Although it is an open label study, a 37% relative reduction of liver fat at 5 weeks, along with a 48% reduction in fasting triglycerides at 4 weeks, suggests that agonism of FGFR1c will result in meaningful liver fat reduction in NASH patients (Shankar et al. 2018).

We hypothesize that EFX, by virtue of its balanced agonism across FGFR1c/2c/3c will act on both liver and adipose tissue to reduce liver fat substantially, in turn mitigating hepatocyte stress. By combining these metabolic improvements with the direct anti-inflammatory and antifibrotic effects evident with FGF21, EFX is expected to deliver clinically meaningful resolution of NASH.

The dose and length of administration of the drug in study AK-US-001-0101 are supported by safety data from nonclinical studies and from prior Phase 1a/1b studies in T2D patients. The primary endpoint of the study will be the absolute change from baseline in hepatic fat
fraction assessed by MRI-PDFF at Week 12. Non-invasive imaging modalities that assess hepatic fat content are acceptable as study endpoints for early Phase 2 trials (Noncirrhotic Nonalcoholic Steatohepatitis With Liver Fibrosis: Developing Drugs for Treatment, Guidance for Industry, December 2018).

The potential to observe early histologic changes at Week 12 is supported by the Phase 2 trial of NGM282. Nineteen subjects with biopsy-confirmed NASH completed 12 weeks of treatment with paired biopsies. Histopathology of 13 (68%) of these biopsies revealed anti-fibrotic activity at Week 12, with biopsies from eight subjects (42%) showing a reduction of ≥ 1 fibrosis stage (Harrison et al. 2019).

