The current regulatory standard for assessing fibrosis referenced in the Guidance for Industry is liver biopsy. As such, improvement in liver fibrosis without worsening of NASH as assessed by liver biopsy will be evaluated in a subset of subjects who show a significant response to treatment (\geq 30% fat reduction by MRI-PDFF at Week 12). Liver biopsy is limited by cost, sampling error, and variability in subjective histopathological interpretation. Due to these limitations, the development and validation of noninvasive markers of liver injury has emerged as a clinical and research priority. A key exploratory objective of the study is to correlate these noninvasive markers with liver histology and determine their utility for monitoring and ultimately predicting histological responses that occur during the course of the study.

Currently there are no approved drugs for the treatment of NASH, and there remains a clear unmet medical need to slow progression of, halt, or reverse NASH. As fibrosis is seen as the strongest predictor of adverse clinical outcomes in NASH, the Main Study will enroll biopsy-proven noncirrhotic NASH patients with (fibrosis stage 1 to 3 and a NAS of \geq 4) and Cohort C will enroll patients with compensated cirrhosis with fibrosis stage 4.

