3. INVESTIGATIONAL PLAN

3.1. Overall Study Design and Plan

This is a Phase 2a, randomized, double-blind, placebo-controlled study evaluating the safety and efficacy of EFX in subjects with NASH.

Main Study: Subjects meeting the study's entry criteria will be randomly assigned in a 1:1:1:1 ratio into 4 treatment groups as shown in Figure 2 below:

Figure 2.Study Schema – Main Study

Randomization will be stratified by baseline hepatic fat fraction (< 15% vs \geq 15%) and F1 fibrosis score. Study drug will be administered subcutaneously once weekly (QW) for a total of 16 weeks. After 16 weeks of treatment, a safety follow-up visit will occur at Week 20. Subjects with \geq 30% relative fat reduction on MRI-PDFF at week 12 will be required to return between weeks 22 - 24 for a repeat liver biopsy and MRI-PDFF.

Cohort C: Subjects meeting the study's entry criteria will be randomly assigned in a 1:2 ratio into 2 treatment groups as shown in Figure 3 below:

Figure 3. Study Schema – Cohort C

Following 16 weeks of treatment, subjects will be given the option to collect an end of treatment biopsy.

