6.7. Liver Biopsy

Main Study:

A liver biopsy must be obtained at screening and between weeks 22-24 (for subjects with \geq 30% relative fat reduction on MRI-PDFF at Week 12) to provide the liver tissue for central reading. All reasonable attempts should be made to acquire a liver biopsy specimen of at least 2.0 cm in length. It is recommended that a 16-gauge needle is used to collect the tissue sample.

A historical biopsy that meets eligibility criteria may be accepted as the screening biopsy if the sample is deemed acceptable for interpretation by the central reader. The historical sample must have been originally obtained within 180 days of the Randomization date and confirm the below criteria:

- Subject was not previously treated for NASH/NAFLD with prohibited concomitant medications (including investigational products) within 6 months of historical biopsy.
- Subject was not previously treated with an Investigational Product within 6 months prior to or at the time of historical biopsy.

If the historical biopsy is not adequate for interpretation by the central reader, or was obtained more than 180 days prior to randomization, a fresh liver biopsy will be collected. Liver biopsies will be sent to a central laboratory and then read by a central reader. The central reader will read all screening biopsies for eligibility.

Cohort C:

A historical biopsy performed within 24 months of the Screening Visit or for those subjects who undergo a liver biopsy for eligibility, the following is required for enrollment:

- Biopsy must be consistent with NASH and cirrhosis as assessed by a local pathologist.
- Subject was not previously treated for NASH/NAFLD (including investigational products unless documentation can be provided that the subject was randomized to placebo) between obtaining the historical biopsy and the Screening visit.

Following 16 weeks of treatment, subjects will be given the option to collect an end of treatment biopsy. Both the historical biopsy sample used to qualify the subject at screening as well as the end of treatment biopsy sample will be shipped for blinded pathology analysis by the central reader.

All Subjects:

If a liver biopsy is performed per standard of care outside of protocol mandated assessments, all possible attempts should be made to submit the biopsy specimen to the central reader for evaluation.

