7.3. Analysis Sets

7.3.1. Efficacy

The primary analysis set for efficacy analyses will be the Full Analysis Set (FAS) which includes all subjects who were randomized into the study.

Subjects who receive a dose of study drug other than that to which they were randomized for the entire duration of treatment will be analyzed according to treatment group to which they were randomized.

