7.6.3. Exploratory Efficacy Analysis

The same efficacy analyses used for the secondary efficacy variables will be used for the exploratory efficacy variables.

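### Main Study NAS response is scored on all randomised subjects although repeat biopsy is scheduled only for Week 12 fat responders, so a liver-fat effect alone can make the histology test significant

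*Protocol*

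**What the plan says.** - **Who is biopsied.** Protocol section 3.1 states that Main Study subjects with a relative fat reduction of at least 30% at Week 12 "will be required to return between weeks 22 - 24 for a repeat liver biopsy and MRI-PDFF". Section 6.7 and the Appendix A footnotes repeat the restriction. The one other route to a post-baseline reading is in section 6.7: "If a liver biopsy is performed per standard of care outside of protocol mandated assessments", the specimen should be sent to the central reader if possible.
- **What is tested.** Section 7.1.1.2 lists NAS response as a secondary endpoint, with no restriction to biopsied subjects. Section 7.6.2 tests it by Fisher's exact test and adds: "Odds ratios, 95% confidence intervals and p-values will be provided. The missing value will be imputed as a non-responder".
- **In whom.** Section 7.3.1: "The primary analysis set for efficacy analyses will be the Full Analysis Set (FAS) which includes all subjects who were randomized into the study". No Main Study text names another set for the NAS test, or separates a biopsy that was never scheduled from one that is missing.
- **What inherits the method.** Section 7.6.3: "The same efficacy analyses used for the secondary efficacy variables will be used for the exploratory efficacy variables". This covers the Main Study fibrosis and NAS proportions at Weeks 22–24.
- **What is disclosed.** Section 1.5 says that fibrosis improvement on biopsy "will be evaluated in a subset of subjects who show a significant response to treatment". The analysis sections do not carry this through.

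**The concern.** Scoring missing as non-response is usually regarded as cautious. That holds when missingness does not favour the active arm. Here the biopsy is absent because the subject lacked a fat response, which is the outcome the drug is expected to change. Placebo therefore loses many more biopsies than EFX, and each lost biopsy counts as a NAS failure.

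Apart from standard-of-care biopsies, the counted event is *fat responder and NAS responder*. The comparison is a valid randomised test of that composite. Its label is the problem: a significant odds ratio for NAS or fibrosis would be read as histologic benefit when part or all of it may restate the MRI result.

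A lesser point has the same cause. Change in fat fraction at Weeks 22–24 is a secondary endpoint (section 7.1.1.2), but that scan is scheduled only for Week 12 responders, and section 7.4 says missing values are in general not imputed. An ANCOVA against placebo at that visit would compare groups selected on outcome.

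**Working it through.** **The plan's own figure.** Section 7.10 gives about 91% power for the fat comparison: 20 per arm, difference 5, SD 5.2, one-sided 5%. The noncentrality is 5 / (5.2 × √(2/20)) = 3.04 on 38 degrees of freedom, giving 91.0%, so the stated figure reproduces. No operating figure is given for the NAS test.

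**Step 1: fat-response rates.** The protocol does not state these, so they are derived from figures it cites.
- Section 1.5 reports an FGF21-analogue trial: "Absolute fat levels in the daily and weekly dosing cohorts fell 6.8% and 5.2%, respectively, compared to 1.3% in the placebo group". The matching relative reductions are 38%, 26% and 6%, which imply baselines of 6.8/0.38 = 17.9, 5.2/0.26 = 20 and 1.3/0.06 = 21.7.
- SD 5.2 and the 5-point design effect come from section 7.10.
- The upper bracket is the largest effect cited in section 1.5, a "placebo-corrected absolute reduction in liver fat of 11.2% at 12 weeks".
- Assumption: changes are normally distributed. With baseline B and mean fall d, P(fat response) = Φ((d − 0.3B)/5.2).

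| Baseline B | Placebo (d = 1.3) | EFX, design effect (d = 6.3) | EFX, larger effect (d = 12.5) |
|---|---|---|---|
| 18 | 21.5% | 56.9% | 91.4% |
| 20 | 18.3% | 52.3% | 89.4% |
| 21.7 | 15.8% | 48.4% | 87.5% |

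Rounded cases carried forward: 55% versus 20%, and 90% versus 20%.

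**Step 2: rejection probability.** Assumptions not in the documents: the true NAS response rate q is the same in both arms, and the test is two-sided at 0.05 (sidedness is not stated; the 95% interval suggests it). There are 20 per arm. The counted rate in an arm with fat-response rate f is P(fat and NAS response), which is f × q under independence. For example, at q = 40% it is 0.55 × 0.40 = 22% on EFX against 0.20 × 0.40 = 8% on placebo. Enumerating both binomials exactly gives the probability that Fisher's test rejects:

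| Case | q = 20% | 30% | 40% | 50% |
|---|---|---|---|---|
| Everyone biopsied | 2.3% | 2.5% | 2.4% | 2.0% |
| Fat 55% vs 20%, independent | 2.9% | 7.9% | 13.5% | 19.0% |
| Fat 90% vs 20%, independent | 14.6% | 31% | 47% | 62% |
| Strongest possible association, either contrast | 2.3% | 6.2% | 19% | 41% |

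**Step 3: dependence.** Steatosis is part of NAS, so independence is a limiting case. With a bivariate normal latent correlation of 0.3 to 0.7 and q from 30% to 50%, rejection is about 9% to 23% for 55% versus 20%, and about 14% to 55% for 90% versus 20%. In the last row of the table the counted rate is min(f, q). The excess vanishes only if every NAS responder is also a fat responder in both arms, which requires q to be no higher than the placebo fat-response rate.

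**Step 4: examples with half of the biopsied subjects responding on NAS in both arms.**
- Fat responders 18/20 and 4/20: counted NAS responders 9/20 versus 2/20, odds ratio (9/11)/(2/18) = 7.4, p = 0.031. Among those biopsied, 9/18 versus 2/4, p = 1.0.
- Fat responders 12/20 and 4/20, near the design effect: 6/20 versus 2/20, p = 0.24. Significance is possible but not assured.

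**The case against.** The strongest reply is that the governing document is absent. The SAP supplied covers Cohort C only, and its section 1 says a separate Main Study SAP exists. Section 7.6.2 does not name the analysis set for the NAS test; *all randomised* comes from reading it with section 7.3.1. The Cohort C SAP analyses histology in a Liver Biopsy Evaluable Analysis Set (section 3.2.8), as counts and percentages by arm (section 3.4.2.5), so the sponsor did not carry the protocol rule over mechanically there. All of this stands as a limit on the finding. It does not change what the protocol prescribes for the Main Study, where nothing provides such a set.

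Second, equal NAS rates alongside a large fat effect may be a hard null to believe, since steatosis contributes to NAS. If the drug affects neither fat nor NAS, the test keeps its size. That is correct, and the rejection rates above should be read as conditional on equal true NAS rates. The p-value still cannot separate a real NAS effect from selection by fat response.

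Third, the size depends on assumptions. No NAS rate is given, and the 90% case joins an effect from one cited trial to the placebo change and baseline of another. For 55% versus 20% at q = 20%, rejection stays under 5% in every case examined. With the 48.4% versus 15.8% contrast and correlation 0.7 it reaches 5.2%.

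Fourth, this is a nominal secondary p-value in a study that section 7.10 calls exploratory, and the biopsy restriction is disclosed. That limits the consequence without correcting the label. Restricting the test to biopsied subjects is not a clean substitute either, because it conditions on a post-randomisation response.

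**Conclusion.** The concern holds for the protocol as written. Following its text tests the composite of Week 12 fat response and NAS response under the name of NAS response, and the exploratory histology proportions inherit the problem. If true NAS rates are equal and independent of fat response, the chance of a significant result rises from about 2% to 8–19% near the design effect, and to 31–62% at the larger cited effect, for NAS rates of 30% to 50%. Positive association changes these figures but does not in general remove the excess. It is negligible near the design effect when the NAS rate is 20% or less. The result rests on the derived fat-response rates, the assumed NAS rates, 20 per arm and a two-sided 5% test. The primary endpoint and its fixed-sequence testing are untouched. This should be fixed; confidence is medium because the Main Study SAP was not seen.

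**What to change.** In sections 7.6.2 and 7.6.3, and the matching synopsis text, do one of the following for the Main Study:

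1. Keep the all-randomised test, but name the endpoint *MRI-PDFF responder and NAS responder* and state that it is not a separate test of histology.
2. Report NAS and fibrosis results by arm among biopsied subjects with exact confidence intervals, labelled as conditional on Week 12 fat response and without a between-arm p-value.

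Under either option, state the analysis set and whether *missing* includes subjects never scheduled for biopsy, and confirm that the Main Study SAP agrees. Report Week 22–24 fat fraction as within-arm durability among Week 12 responders, not as an ANCOVA against placebo.

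The cost is wording in two documents and no extra biopsies. The sponsor relabels or gives up one secondary p-value. Under option 2 the placebo estimate is very imprecise: at a 20% fat-response rate about 0.20 × 20 = 4 placebo subjects would be biopsied, and 2 of 4 has an exact 95% interval of about 7% to 93%.
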